4.2 Overview of Study Design

A prospective, single arm, open label, multi-center, trial to evaluate the safety and effectiveness of the Interscope EndoRotor® Resection System in subjects requiring direct endoscopic necrosectomy with walled off pancreatic necrosis (WOPN). Total enrollment of 30 subjects with at least 15 enrolled in the US.

Subjects will be debrided with the EndoRotor at least 2 days following initial stent placement with a maximum of 4 EndoRotor procedures. A minimum of 2 days is required between each EndoRotor procedure and all procedures need to be completed within a 14 (+7/-0) day period. Follow up is completed to 21 (+/-7) days after first EndoRotor debridement procedure.

4.3 Primary Endpoint

The primary endpoint of this study is the freedom from major complications. The safety endpoint will include an assessment of the safety of the EndoRotor when performing endoscopic necrosectomy. For the purpose of this study, the safety evaluation shall include complications associated with endoscopic necrosectomy through the 21 (+/-7) day follow-up period. Potential endoscopic complications include perforation and bleeding.

4.4 Secondary Endpoints

- Successful clearance of necrosis in the collection treated during direct endoscopic necrosectomy where success is defined as at least 70% of the necrotic debris in the WOPN cavity is removed

based on CT evaluation of the cavity at the 21 (+/-7) day follow up visit.

- Assessment of total procedure time to achieve clearance of necrosis for all procedures
- Assessment of adequacy of debridement
- Assessment of total number of procedures to achieve clearance of necrosis
- Assessment of length of hospital stay and utilization
- SF-36 Questionnaire

4.5 Clinical Sites & Enrollment

Up to six (6) research sites in the United States and up to four (4) research sites in the European Union will participate in this trial. The sites will enroll a total of 30 subjects meeting all inclusion and exclusion criteria to reach a total of 30 evaluable subjects. Once the informed consent process is completed and final study eligibility has been confirmed, the patient will have the EndoRotor direct endoscopic necrosectomy.

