4.9 Subject Screening

Following placement of stent and determination of need for necrosectomy study eligibility is confirmed and the patient will receive the EndoRotor® intervention. The patient will be enrolled upon insertion of the catheter into the endoscope. Screening shall include:

- Pregnancy test – within 1 day of the procedure.
- Medical clearance in advance of the procedure.
- WOPN resulting from necrotizing pancreatitis per high resolution vascular CT with the characteristics per the 2012 Revised Atlanta Classification.
- Imaging suggestive of greater than 30% necrotic material
- WOPN size ≥ 6 cm and ≤ 22 cm

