4.14 Study Withdrawal & Lost to Follow Up

Study participation is voluntary and subjects may withdraw their consent at any time. **ALL** enrolled subjects and their status in the study will be included in the study reports.

- **Treated and Study Criteria Not Met:** Subjects who are enrolled and treated, but who are later discovered to not meet all of the study criteria, will remain in the study and complete all of the study testing and follow-up requirements. A protocol deviation will be completed for study subjects who are

found to be ineligible after enrollment. These subjects may be excluded from the Per Protocol analysis depending upon the nature of the protocol deviation.

- **Patient Withdrawal:** Participation in any clinical investigation is voluntary and a patient is allowed to discontinue their participation at any time. Subjects may withdraw at their own discretion with or without reason and without any impact on their continued medical care. If a patient voluntarily withdraws from the study, no additional medical data will be collected, and the patient will not continue in the study.
- Subjects who withdraw from the study will not be replaced; however, if a patient withdraws their consent **BEFORE** being treated with the study device (before insertion of the catheter into the endoscope), and/or before the 21 (+/-7) day follow-up, he or she will not be included in the analysis.
- **Investigator Termination:** The site Investigator may terminate the patient’s procedure if it is in the patient’s best interest not to continue; however, the patient is withdrawn from the study and will not be included in the analysis.
- **Lost-to-Follow-up:** A patient who does not complete follow-up requirements and does not officially withdraw from the study is considered lost-to-follow-up. This does not apply to missed visits where the patient misses one of the follow-up contact time points but completes the subsequent one. In order to consider a patient lost-to-follow-up, site personnel should make all reasonable efforts to locate and communicate with the patient. All attempts to contact the patient must be recorded in the study notes, including the date, time, and name of site personnel who have attempted to contact the patient.

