7.3 Sample Size

This study will enroll a total of 30 subjects. Sample size determination is based on the nature and objective of this study and not statistical considerations. The data will be sufficient to provide an assessment of the safety profile of the EndoRotor for DEN in WOPN as well as provide initial efficacy data to support an evaluation of the benefit/risk profile.

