7.5 Missing Data

Missing data within this subject cohort is expected to occur at a low rate. All efforts will be made to prevent the occurrence of missing data. Site training and regular monitoring will help to minimize missing data. Due to the sample size and nature of this pilot study, there will be no imputation of missing data. In other words, analyses will be based only on available data.

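### Section 4.5 sets 30 evaluable subjects from 30 enrolled, but Section 4.14 bars replacing withdrawals and drops them from the analysis, so one such loss leaves at most 29

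*Combined protocol and SAP*

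**What the plan says.** - **Size.** Section 4.5 (Clinical Sites & Enrollment): "The sites will enroll a total of 30 subjects meeting all inclusion and exclusion criteria to reach a total of 30 evaluable subjects". The Protocol Summary and Sections 4.2, 4.7 and 7.3 give the same enrollment total; in 7.3 it reads "This study will enroll a total of 30 subjects". None adds an allowance for losses.
- **Basis of the size.** Section 7.3: "Sample size determination is based on the nature and objective of this study and not statistical considerations".
- **Start of the count.** Section 4.9: "The patient will be enrolled upon insertion of the catheter into the endoscope".
- **Replacement.** Section 4.14: "Subjects who withdraw from the study will not be replaced".
- **Exclusion.** Section 4.14 continues that, for a patient who withdraws consent before treatment "and/or before the 21 (+/-7) day follow-up, he or she will not be included in the analysis". Where the investigator terminates the procedure, "the patient is withdrawn from the study and will not be included in the analysis".
- **Missing data.** Section 7.5: "Missing data within this subject cohort is expected to occur at a low rate". It gives no rate. Missing values are not imputed, and analyses use the data available.
- **Populations.** The Primary Analysis row of the Protocol Summary takes subjects who are enrolled, eligible and treated. Section 7.2 defines the Safety population as everyone in whom the procedure was attempted. Neither requires completion of follow-up, and neither uses or defines the term evaluable.

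**The concern.** The evaluable number in 4.5 equals the enrolled number, so it assumes no losses at all. Section 4.14 sets out how losses are handled, and 7.5 expects some missing data. The two sections therefore give different denominators as soon as one enrolled subject withdraws or is terminated: 4.5 says 30, and 4.14 gives 29 or fewer.

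What is at stake is which subjects are counted, more than power. The trial has a single arm, and freedom from major complications is its primary endpoint. With about 30 subjects, each one is worth roughly 3 percentage points (1/30 = 3.3%). A reader of the final report should know beforehand whether a treated subject who left early is in the safety denominator. At present 4.5, 4.14, 7.2 and the Protocol Summary do not give one answer.

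**Working it through.** **Inputs from the documents.** Enrolled 30; evaluable 30 (4.5). Withdrawals not replaced; withdrawals before day 21 and investigator terminations excluded from the analysis (4.14). No imputation, and no numerical loss rate (7.5). No alpha, power or effect size lies behind the 30 (7.3), so there is no power calculation to reproduce. Only the step from enrolled to evaluable can be checked.

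**Step 1: the plan's own figure.** Evaluable = enrolled × (1 − d), where d is the proportion lost after enrollment. 30 × (1 − d) = 30 only at d = 0. The figure is reproduced, but only with zero loss.

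**Step 2: effect of losses under 4.14.** With no replacement and enrollment fixed at 30, 1, 2 or 3 exclusions leave 30 − 1 = 29, 30 − 2 = 28 or 30 − 3 = 27. A candidate who withdraws before the catheter is inserted has not been enrolled under 4.9 and uses none of the 30 places, so only later losses matter here.

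**Step 3: how likely zero loss is.** The documents give no rate, so d is an assumption, with losses taken as independent between subjects. The chance that all 30 remain is (1 − d)^30.

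| Assumed loss d | (1 − d)^30 | Expected evaluable, 30 × (1 − d) |
|---|---|---|
| 1% | 0.99^30 = 0.7397 (74%) | 29.7 |
| 2% | 0.98^30 = 0.5455 (55%) | 29.4 |
| 5% | 0.95^30 = 0.2146 (21%) | 28.5 |
| 10% | 0.90^30 = 0.0424 (4%) | 27.0 |

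**Step 4: effect on precision.** With zero events in n subjects, the exact two-sided 95% upper bound is 1 − 0.025^(1/n).

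- n = 30: 11.6%
- n = 29: 11.9%
- n = 28: 12.3%
- n = 27: 12.8%

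Three losses raise the bound by 12.8 − 11.6 = 1.2 percentage points.

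**Step 5: can a definition of evaluable rescue the 30?**

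- If it means having a day-21 CT, which the clearance endpoint needs (4.4, 5.5), each missing scan takes one away, because 7.5 does not impute.
- If it means included in the analysis under 4.14, each withdrawal before day 21 and each investigator termination takes one away.
- If it means eligible and treated (Protocol Summary), or procedure attempted (7.2), the 30 survives later losses. But those populations then contain subjects whom 4.14 says are not analysed.

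The third reading is the only one that keeps 30 after a loss, and it contradicts 4.14.

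**The case against.** The strongest defence is that evaluable in 4.5 means eligible and treated. The sentence itself speaks of subjects who satisfy the entry criteria, the Protocol Summary defines its primary analysis in similar terms, and enrollment happens at catheter insertion. On that reading 30 enrolled gives 30 evaluable, whatever happens afterwards. This is a fair reading and it softens the point. It does not remove it: the exclusions in 4.14 name no population and so cut across this one, and the clearance endpoint still needs a scan at day 21.

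It is also right that the size is not statistically derived, that the safety analysis is descriptive, and that a few losses barely affect precision. That limits the weight of the point.

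A reader might infer more than the documents support:

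- **That sites would have to replace dropouts with completers to keep the 30.** No section plans topping up. Section 4.14 forbids replacement of withdrawals, and the fixed total leaves no room for it otherwise. The 30 is also a trial-wide total over up to ten sites (six US, four EU), so no single site holds that target. Any favourable bias would come from the exclusions in 4.14, which operate without replacement.
- **That deaths and losses to follow-up are also removed from the analysis.** Section 4.14 excludes withdrawals and investigator terminations only. A fatal event related to the device or procedure within the follow-up window counts in the 7.4.2 safety endpoint.
- **That the plan's claim of sufficient data fails.** Sections 4.7 and 7.3 attach that claim to 30 enrolled, not 30 evaluable, and the design does deliver 30 enrolled.

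**Conclusion.** The point holds as an inconsistency in the current text. Thirty evaluable from 30 enrolled requires zero post-enrollment exclusions under 4.14 and, for the clearance endpoint, zero missing day-21 scans. One withdrawal or termination gives at most 29, with no permitted route back to 30.

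At assumed independent loss of 1% to 10%, the chance of keeping all 30 falls from 74% to 4%. Those rates are illustrative; the plan says only that missing data should be low. The cost in precision is small, about 1.2 percentage points on the zero-event upper bound for three losses. The reason to correct the text is that the safety denominator is ambiguous and the stated evaluable number cannot be relied on. The documents do not support a claim that dropouts would be swapped for completers, nor any figure for the resulting bias.

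**What to change.** 1. In 4.5, delete the closing clause that sets the evaluable total. State that 30 subjects are enrolled and treated across the trial, that each is counted at catheter insertion as in 4.9, that none is replaced after insertion for any reason, and that candidates lost before insertion do not count towards the 30. Align 5.3.3, 5.3.4 and Appendix 1, which use enrollment as though it could precede treatment.
2. In 4.14, amend the exclusions so that they agree with 7.2. All 30 subjects stay in the Safety denominator, including those who withdraw or are terminated after insertion, with data up to the point at which they left.
3. In 7.4.3 or 7.5, state that the day-21 CT endpoint may have fewer than 30 subjects, and that the number lost and the reasons will be reported. If an expected number is given, it should be the sponsor's own estimate, labelled as an assumption.

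The cost is a few sentences, with no additional patients. The downside is that the stated evaluable number becomes slightly less favourable. An enrollment allowance would be the alternative: 30/(1 − d), rounded up, gives 32 at an assumed 5% loss and 34 at 10%. It is hard to justify when the 30 has no statistical basis and precision is hardly affected.

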4.6 Study Duration & Follow-Up

Total study duration is expected to be approximately 180 days assuming enrollment occurs in 90 days, subjects are followed and assessed at 21 (+/-7) days post procedure and allowing for 60 days for data collection and reporting.

4.7 Patient Population / Sample Size

This study is primarily designed as a safety evaluation and will enroll a total of 30 subjects. A minimum of 15 subjects will be enrolled at centers in the US. Although a primary efficacy and safety endpoint is specified, these endpoints are not statistically powered. However, for regulatory purposes, the data generated from this study is sufficient to demonstrate the benefit risk profile of the EndoRotor for this indication.

4.8 Subject Recruitment

The subjects will be recruited from the clinical practices of the investigators. Due to the number of patients with WOPN subjects they follow and are referred each month, there may not be a need to advertise. These centers are major referral centers for advanced cases such as WOPN. Subjects who require direct endoscopic necrosectomy will be told of the study and asked if they would be interested in participating.

4.9 Subject Screening

Following placement of stent and determination of need for necrosectomy study eligibility is confirmed and the patient will receive the EndoRotor® intervention. The patient will be enrolled upon insertion of the catheter into the endoscope. Screening shall include:

- Pregnancy test – within 1 day of the procedure.
- Medical clearance in advance of the procedure.
- WOPN resulting from necrotizing pancreatitis per high resolution vascular CT with the characteristics per the 2012 Revised Atlanta Classification.
- Imaging suggestive of greater than 30% necrotic material
- WOPN size ≥ 6 cm and ≤ 22 cm

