5.3.3 Screen Failures

Enrolled subjects failing to meet inclusion / exclusion criteria at the time of index procedure will not be treated with the EndoRotor® device and; therefore, are classified as screen failures. Any baseline study data captured in the CRFs will be collected. Only subjects in whom the EndoRotor® catheter will be followed and study data analyzed.

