5.3.4 Index Procedure

The investigators shall follow the technique described by the manufacturer's instructions as provided in the Instructions for Use. Following stent placement and once the clinician determined removal of necrotic debris should be completed, direct endoscopic necrosectomy of the WOPN will be performed within 2 weeks of enrollment with video documentation of the necrotic debris at start of the procedure. For patients with LAMS, a therapeutic gastroscope must be able to pass through the LAMS necessitating a minimum stent diameter to accommodate the gastroscope such as a 15mm. If a LAMS is used, it must be removed within 60 days per manufacturer's labeled instructions for use.

The EndoRotor® will be set-up and used to resect the WOPN. The resection is removes all accessible necrotic debris wherever the endoscope can provide access. No resection is performed on the pancreatic wall during this procedure. Multiple debridement procedures can be performed to remove necrotic tissue as required.

The EndoRotor® is set to either High Speed (1700 RPM) or low speed (1000 RPM) based on user preference and the vacuum is set to between 550 mmHg of negative pressure. The endoscopist will start the EndoRotor® motor using the left foot pedal and will activate the cutting by depressing and holding the right pedal down for as long as he wants to resect. The technique is repeated until the entire gross visible necrotic debris has been removed to present a cavity clear of necrosis.

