7.4.2 Safety Analysis

All safety data will be displayed and analyzed using descriptive statistical methods. No formal inferential analysis is planned for safety comparisons. The safety endpoint is the absence of any device or procedure related serious significant adverse events (SAEs) within the 21 (+/-7) days following EndoRotor procedure. These will be presented overall and by system organ class and preferred term (PT). This will be conducted on the Safety analysis set overall. Subjects who experience more than one event in a given System Organ Class (SOC) and PT will be counted once within that SOC and PT. The total number of events and the number and percentage of subjects with each event will be reported.

Adverse Events: AEs, SAEs and UADEs will be coded using MedDRA. Treatment Emergent AEs, SAEs and UADEs are defined as events starting or worsening after start of the procedure. The number and percent of patients with Treatment Emergent AEs, SAEs and UADEs will be summarized overall and by primary SOC and preferred term (PT). Subjects who experience more than one event in a given SOC and PT will be counted once within that SOC and PT.

The number and percent of subjects with treatment emergent AEs, UADEs and SAEs will be further presented by severity and by relationship to the device or procedure. In tabulating the severity of AEs on a per subject basis, the greatest severity will be assigned to a subject should there be more than one occurrence of the same AE with different reported severities. Relationship will be categorized as unrelated, possibly, probably and definitely related. The highest level of association will be reported for subjects with different relationships for the same AE.

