10.5 Reporting of Adverse Events

All adverse events, including SAE’s and UADE’s, will be monitored from the time of enrollment through the

study exit. A description of the event, including the start date, resolution date, action taken, and the outcome shall be provided, along with the Investigator's assessment of the relationship between the AE and the study device and procedure.

All AE's should be followed until the event is resolved or judged to be clinically stable. The clinical site should plan to provide additional, relevant AE follow-up information to the Sponsor upon request.

All SAEs, DRSAEs, and UADE's must be reported to the Sponsor and/or CRO and the primary Investigator at the site **within 24 hours** of the Investigator becoming aware of the event. Additionally, the Investigator should notify their IRB, and local/national authorities as required, within their specified timeframes. The Sponsor and CRO will decide whether all of the local Investigators need to be informed immediately, or whether this can be postponed until the next regularly scheduled study update.

A completed SAE CRF **must** be uploaded to the Sponsor's secure web server **within 7 days of the event**. The minimum required data to be recorded for an SAE includes: date of event, type of event, duration of event, severity, seriousness, action taken, outcome, causality and relationship to the Interscope device and procedure. In the case of a DRSAE, whenever possible, the device involved in the failure or malfunction is to be returned to Interscope for analysis.

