APPENDIX 1 – SCHEDULE OF STUDY ASSESSMENTS

A schedule of study assessments is provided below.

	Baseline	Index Procedure (Day 0)²	Procedures 2 through 4 14 (+7/-0) Days³	Discharge	21 (±7) Days⁴
Confirm Eligibility	X	X			
Informed Consent	X				
Demographics	X				
Medical History	X				
Physical Examination	X				X
SF-36	X				X
Pregnancy Test ¹	X				
EndoRotor® Procedure		X	X		
CT Imaging (Standard of Care)	X				X
Adverse Event Assessment		X	X	X	X

¹ Urine pregnancy test for female of child bearing potential within 1 day of procedure.

² The index procedure must be done within 2 weeks of enrollment with outpatient video documentation of before and final results from procedure.

³ Procedures 2 through 4 at 14 (+7/-0) days is not required if there is at least 70% removal of accessible necrotic debris in the collection being treated.

⁴ Visit based on 21 (+/-7) days from last EndoRotor procedure

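### Enrollment at catheter insertion, with AE monitoring tied to enrollment, can lose a procedure-related event that ends the index session before insertion; other sections place enrollment before the procedure

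*Combined protocol and SAP*

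**What the plan says.** **Enrollment point.** Section 4.9: "The patient will be enrolled upon insertion of the catheter into the endoscope". Three other places put it earlier:

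- Section 5.3.4: the necrosectomy "will be performed within 2 weeks of enrollment".
- Appendix 1, footnote 2: "The index procedure must be done within 2 weeks of enrollment".
- Section 5.3.3: "Enrolled subjects failing to meet inclusion / exclusion criteria at the time of index procedure will not be treated". It then classes these people as screen failures.

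**Start of AE collection.** Section 10.5 says that all adverse events "will be monitored from the time of enrollment", up to study exit. Section 7.4.2 defines treatment-emergent events as "events starting or worsening after start of the procedure".

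**Who is analyzed.** The Safety population in 7.2 is the subjects in whom the EndoRotor procedure was attempted; 'attempted' is not defined. The last sentence of 5.3.3 ties follow-up and analysis to the catheter, although its verb is missing. Section 4.14 leaves out subjects who withdraw consent before catheter insertion. It also withdraws, and leaves out, subjects whose procedure the investigator terminates.

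**Endpoint.** Section 7.4.2 defines the safety endpoint as freedom from serious events related to either the device or the procedure.

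**The concern.** Section 4.7 describes the trial as mainly a safety evaluation. It has one arm, about 30 subjects and a descriptive safety analysis, so the raw event count is the main result. The endpoint includes procedure-related harm, and 6.1 lists stent dislodgment, injury to the GI tract, heart attack, pneumonia and stroke among the risks. Some of these can arise before the device is introduced.

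If the rule that admits a subject to the study takes effect only once the catheter is in the endoscope, a harm serious enough to stop the session before then can remove its own subject from both numerator and denominator. Separately, sites cannot apply 4.9, 5.3.3, 5.3.4 and Appendix 1 together, so it is unclear when a subject counts toward the 30.

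**Working it through.** The plan gives no figure to reproduce: 7.3 states that the sample size has no statistical basis. The check is a comparison of sections, followed by an illustration.

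**Step 1. Order of events.** Section 1.1 says that the device works through the endoscope's instrument channel. Section 5.3.4 requires the gastroscope to pass through the stent in LAMS patients. Section 5.3.5 records the time of endoscope insertion and the start of EndoRotor use. Sedation and scope passage would therefore normally precede catheter insertion. This is an inference; no section states the order.

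**Step 2. The enrollment points conflict.** Under 4.9, enrollment happens during the index session. The interval from enrollment to index procedure is then essentially zero for everyone, and the 2-week limit in 5.3.4 and Appendix 1 can never bind. Under 5.3.3, a subject can be enrolled and never treated, which 4.9 does not allow. This conflict exists whether or not any adverse event occurs.

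**Step 3. Three cases for an event before catheter insertion.**

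| Case | 4.9 and 10.5 | Other sections | Result |
|---|---|---|---|
| Index session, catheter inserted later | Event precedes enrollment and monitoring | 7.4.2 counts from procedure start; Appendix 1 assesses AEs at the index procedure; 5.3.5 records any AE | Probably captured, contrary to 10.5 |
| Index session, abandoned before insertion | Not enrolled, not monitored | 5.3.3 apparently gives no follow-up; 4.14 may exclude; 7.2 arguably includes as attempted | Can be lost |
| Procedures 2 to 4 | Already enrolled and monitored | No conflict on AE start | Captured |

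Only the second case is a firm gap. Moving the enrollment point alone does not close it, because the investigator-termination rule in 4.14 does not depend on when enrollment occurred.

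**Step 4. Size if one event is lost.** The counts are assumed. Exact (Clopper-Pearson) two-sided 95% limits for x events in n subjects are: lower = 0.025 quantile of Beta(x, n − x + 1); upper = 0.975 quantile of Beta(x + 1, n − x). The lower limit is 0 when x = 0.

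- Counted, 1/31: 1 ÷ 31 = 3.2%. Lower, from Beta(1, 31), 0.1%; upper, from Beta(2, 30), 16.7%.
- Lost, 0/30: 0%. Upper = 1 − 0.025^(1/30) = 11.6%.
- From a higher base, counted, 4/31: 12.9% (3.6 to 29.8%).
- From that base, lost, 3/30: 10.0% (2.1 to 26.5%).

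**The case against.** The strongest reply is that the safety analysis does not run on enrolled subjects. It runs on the 7.2 Safety population, within a Study population of everyone who consented. With the 7.4.2 definition, the Appendix 1 schedule and the 5.3.5 record, an event under sedation is picked up whenever the catheter is subsequently used. This stands. A reader might infer that every procedure-related event during sedation or scope passage falls outside the study. The documents do not support that: it is wrong for procedures 2 to 4 and doubtful for completed index sessions. Nor are these people outside the study altogether; they have consented but are not enrolled.

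The reply does not rescue the abandoned session. 'Attempted' is undefined, 4.14 treats catheter insertion as the start of treatment, and membership of a population cannot restore events that 10.5 did not require sites to collect.

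Three further objections have some force:

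- Starting at device introduction is a defensible choice for a device-exposed rate, and adding unexposed subjects can dilute that rate. But the endpoint also covers procedure-related events, so both rates should be visible.
- Section 5.3.3 may be using 'enrolled' loosely for 'consented'. That would explain its wording, but it would not reconcile the 2-week window with 4.9.
- The illustration shows only what any single event does in about 30 subjects, and the plan specifies no confidence intervals. That is correct; it is a scale, not an estimate.

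**Conclusion.** The enrollment point and the AE start point are each stated inconsistently, and the 2-week window cannot operate under 4.9. That follows from the text alone.

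The loss of safety data is confined to an index session abandoned before catheter insertion because of a procedure-related event. It rests on the inferred order of steps and on reading 5.3.3 and 4.14 as excluding such a subject. If one occurs, the reported rate could be 0/30 instead of 1/31, with the upper limit falling from 16.7% to 11.6%. The documents give no basis for how often this would happen, so no bias can be estimated. The point should be corrected because safety is the primary purpose and the change is small; it does not undermine the safety analysis as a whole.

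**What to change.** 1. In 10.5, start AE collection at the start of the index endoscopic session (sedation or endoscope insertion) undertaken with intent to use the EndoRotor, in line with 7.4.2.
2. In 7.2, define 'attempted' in the same way.
3. In 4.14 and 5.3.3, state that investigator termination or withdrawal after that point does not remove data already collected from the Safety analysis. This concerns analysis only and leaves the decision to stop a procedure untouched. Complete the unfinished sentence in 5.3.3.
4. Report pre-insertion (unexposed) cases separately as well, so that the device-exposed rate remains visible.
5. Reconcile 4.9, 5.3.3, 5.3.4, 10.5 and Appendix 1 to one enrollment point, and reconcile the 2-week window with it.

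**Cost.** This is mostly wording, but it needs some new data. Abandoned-session subjects would need AE follow-up and a visit anchor, because 5.4.2 and Appendix 1 footnote 4 date the 21-day visit from the last EndoRotor procedure, which they would not have had. The safety denominator may grow slightly.
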